10.1.2 Duration of Response

DOR will be computed for SAF subjects with a confirmed overall response of iCR or iPR (as per iRECIST). DOR (in months) will be defined as:

$$(censoring date OR date of iUPD followed by confirmation or death - date of first response + 1) / 30.4375.$$

Event and censoring rules for DOR are detailed in [APPENDIX 2. CENSORING RULES: DOR and PFS](#).

Kaplan-Meier estimates for DOR will be calculated for each cohort/arm (including, Total: Cohort 3: CyPep-1 5.0 mg/mL + Arm A: CyPep-1 5.0 mg/mL Monotherapy), and 75th, 50th and 25th percentiles presented, along with 95% confidence intervals. Number (%) of subjects with an event and number (%) censored will be reported for each cohort/arm. 3-month, 6-month, and 1-year estimates with associated 95% CIs will also be presented.

DOR data will be presented in listings for SAF.

10.1.3 Time to Response

Time to response will be computed for SAF subjects with a confirmed overall response of iCR or iPR (as per iRECIST). TTR (in months) will be computed as:

$$(date of first response - treatment start date + 1) / 30.4375.$$

TTR will be analyzed based on the Kaplan-Meier methods described for DOR, except for not presenting number (%) of subjects censored which is not applicable for TTR analyses.

TTR derived data will be presented in listings for SAF.

10.1.4 Duration of Stable Disease

Duration of stable disease will be computed for SAF subjects as:

Statistical Analysis Plan

SMS-0571/CyPep-1

V3.0 Final

04-Jun-2024

(censoring date OR date of iUPD followed by confirmation) – treatment start date + 1) / 30.4375.

Event and censoring rules for duration of stable disease are detailed in [APPENDIX 3. CENSORING RULES: DURATION OF STABLE DISEASE](#).

Duration of stable disease will be analyzed based on the Kaplan-Meier methods described for DOR.

Duration of stable disease derived data will be presented in listings for SAF.

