10.1 Secondary Efficacy Analyses

10.1.1 ORR in All Lesions (iRECIST)

A subject's best overall response (BOR) is determined by the highest qualitative value assessed during the study given a hierarchy of overall response results: iCR > iPR > iSD > iUPD > iCPD > NE. Note that even though iUPD is presented before iCPD in iRECIST hierarchy, in case iCPD occurs, it always overwrites iUPD for BOR derivation. A BOR of iCR or iPR requires confirmation of response at least 28 days after the date of the initial response in this non-randomized study (as per RECIST 1.1). BOR will be based on assessments collected after the treatment start date until confirmed disease progression (iCPD) or start of new anticancer therapy, whichever occurs earlier. BOR will be summarized descriptively by cohort/arm (including, Cohort 3: CyPep-1 5.0 mg/mL + Arm A: CyPep-1 5.0 mg/mL Monotherapy) for the SAF.

Secondary efficacy outcome is the objective response rate in all lesions (injected and non-injected) based on iRECIST. ORR will be defined as the percentage of subjects with a BOR of iCR or iPR. The ORR will be summarized by cohort/arm (including, Cohort 3: CyPep-1 5.0 mg/mL + Arm A: CyPep-1 5.0 mg/mL Monotherapy) including 95% 2-sided Clopper-Pearson CIs.

A waterfall plot of maximum percentage reduction from baseline in target lesion sum of diameters (mm) by best overall response will be provided for the SAF. A spider plot of percent change from baseline in target lesion sum of diameter measurements by best overall response will also be provided for the SAF. Only post-baseline data until an overall response of iCPD or start of new anticancer therapy will be included in the figures. In case a lesion is NE at a certain timepoint, sum of diameters will not be presented for that timepoint (in line with RECIST 1.1 recommendation).

A swimmer plot of iRECIST response assessment results will also be created for SAF.

Response evaluation data (including lesions measured, sum of diameters, iRECIST evaluation, maximum reduction in target lesion sum of diameters) will be listed for SAF. BOR and objective response will be listed for SAF.

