10.2.2 Survival

Overall survival (in months) is defined as the time from start of study treatment to the date of death:

(censoring date OR date of death – treatment start date + 1) / 30.4375.

Subjects who do not die will be censored at the last known alive date, i.e., at the date of last study visit or the latest survival follow up call, whichever occurs later. SAF will be used for the evaluation of OS.

Progression-free survival is defined as the time from treatment start until disease relapse or disease progression (based on all lesions, using iRECIST) or death due to any cause, whichever occurs earliest:

(date of iUPD followed by confirmation or death – treatment start date + 1) / 30.4375.

Event and censoring rules for PFS are detailed in [APPENDIX 2. CENSORING RULES: DOR and PFS](#). SAF will be used for the evaluation of PFS.

OS and PFS will be analyzed based on the Kaplan-Meier methods described for DOR.

OS will further be presented (both in tables and on Kaplan-Meier plots) by RMH prognostic score at baseline and GRIM-score at baseline, separately. Subjects with missing RMH prognostic score and GRIM-score values at baseline will be excluded. For the purpose of this exploratory analysis, subjects from all cohorts/arms will be pooled into one group (Total: Phase I + IIa). The analysis will be run including and excluding subjects with adrenocortical carcinoma (ACC) diagnosis. Subjects with ACC diagnosis will be identified based on coded value (i.e., MedDRA PT) of "Adrenocortical carcinoma" corresponding to *Histological type* reported on the *Primary Diagnosis* section of the *Primary Cancer eCRF* page. The aim of this analysis is to further validate the prognostic properties of RMH prognostic score and GRIM-score for population under study.

By-subject data will be listed.

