13.3 APPENDIX 3. CENSORING RULES: DURATION OF STABLE DISEASE

Censoring rules for duration of stable disease are presented in [Table 9](#) below.

Table 9. Censoring Rules for Duration of Stable Disease

#	Situation	Date of Event (PD) or Censoring	Outcome: Event (PD) or Censored
1	No (or inadequate) baseline tumor assessments and the patient has not died	Treatment Start Date	Censored
2	No post-baseline assessments	Treatment Start Date	Censored
3	iUPD followed by discontinuation due to clinical disease progression, radiological disease progression or death within 8 weeks	Date of assessment of progression ¹	Event
4	iUPD without subsequent iSD, iPR or iCPD and followed by:	Date of assessment of progression ¹	Event
	1. Treatment discontinuation due to clinical instability (i.e., clinical disease progression, radiological disease progression). 2. No further response assessments (due to subject refusal, protocol non-compliance). 3. Next timepoint responses all equal to iUPD.		
5	iCPD documented between scheduled visits	Date of assessment of progression ¹	Event
6	No iUPD as described in #3 and #4, no iCPD and no new protocol excluded anticancer treatment documented	Date of last 'adequate' assessment of response ²	Censored
7	No iUPD as described in #3 and #4, no iCPD and new protocol excluded anticancer treatment documented	Date of last 'adequate' assessment of response ² on or prior to starting anticancer therapy	Censored
8	New protocol excluded anticancer treatment started (prior to iUPD as described in #3 and #4, iCPD) ³	Date of last 'adequate' assessment of response ² on or prior to starting anticancer therapy	Censored
9	Death before first iCPD assessment	Date of last 'adequate' assessment of response ²	Censored
10	Progression after two missed visits (with 1-week window) where last assessment is not iUPD	Date of last 'adequate' assessment of response ² prior to missed assessments	Censored

¹The earliest of

- (i) Date of radiological assessment showing new lesion (if progression is based on new lesion); or
- (ii) Date of radiological assessment showing unequivocal progression in non-target lesions, or
- (iii) Date of last radiological assessment of measured lesions (if progression is based on increase in sum of measured lesions).

²An adequate assessment is defined as a radiological assessment where iCR, iPR, or iSD was determined.

Statistical Analysis Plan

SMS-0571/CyPep-1
V3.0 Final
04-Jun-2024

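### Duration of stable disease (SAP 10.1.4) is computed for every treated subject, whether or not stable disease was seen, so the curve is time to progression for the whole arm

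*SAP*

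**What the plan says.** Duration of stable disease is a secondary endpoint (Protocol 2.2.2, SAP 5.2.2). The protocol does not define its population, so SAP 10.1.4 carries the definition: "Duration of stable disease will be computed for SAF subjects as", followed by the time from treatment start to a censoring date or to an iUPD followed by confirmation, analysed by the Kaplan-Meier methods used for DOR. The SAF (SAP 7.2.2) is everyone treated.

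The two preceding sections set a condition on response:

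- SAP 10.1.2: "DOR will be computed for SAF subjects with a confirmed overall response of iCR or iPR".
- SAP 10.1.3: "Time to response will be computed for SAF subjects with a confirmed overall response of iCR or iPR".

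Table 9 (SAP Appendix 3) lists events and censoring for stable disease. Row 3 makes an event of "iUPD followed by discontinuation due to clinical disease progression, radiological disease progression or death within 8 weeks". Row 4 does so for "iUPD without subsequent iSD, iPR or iCPD and followed by" one of three listed circumstances. Row 9, "Death before first iCPD assessment", is censored at the last adequate assessment. Row 2 censors subjects with no post-baseline scan at treatment start. Footnote 2 counts iCR and iPR scans as adequate alongside iSD.

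For PFS, SAP 10.2.2 states: "Progression-free survival is defined as the time from treatment start until disease relapse or disease progression", or death.

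**The concern.** A duration of stable disease describes how long stable disease lasted in subjects who had it. The rule in 10.1.4 also takes in subjects who progressed at their first scan and subjects who responded. The reported figure then mixes two things: how many subjects were still free of progression at the first scan, and how long those subjects stayed so. A reader of the results table would take the median and the 3-month, 6-month and 1-year estimates as the length of stable disease, when they are close to a second PFS analysis. SAP 4.3 records no discrepancy with the protocol, so nothing alerts the reader to the difference.

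**Working it through.** The plan states no median, rate or power for this endpoint, so there is no figure of its own to reproduce.

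**1. Is a restriction supplied elsewhere?** No. Rows 3 and 4 of Table 9 require no earlier iSD before an iUPD counts. No row removes a subject who never had iSD. Footnote 2 lets responders contribute time. SAP 8.8 (missed assessments) and 8.13 (pointer to the censoring tables) are silent on it.

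**2. How does it differ from PFS?** The analysis set (SAF), origin (treatment start) and estimator are the same. The main difference is death. Table 8 counts a death before iCPD as an event on the date of death, whereas Table 9 row 9 censors it. A death with no post-baseline scan falls under row 2 and is censored on day 1. A death within 8 weeks of an iUPD remains an event under row 3, dated at the progression assessment.

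**3. What does progression at the first scan contribute?** Protocol 6.2 sets the first scan at 8 weeks ± 3 days. With the SAP formula:

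- on schedule: (56 + 1)/30.4375 = 1.87 months
- 3 days early: (53 + 1)/30.4375 = 1.77 months
- 3 days late: (59 + 1)/30.4375 = 1.97 months

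**4. When does that value become the arm's median?** When more than half of the scanned subjects progress at that scan. Subjects without a post-baseline scan are censored on day 1 and leave the risk set before any event. Let c be the share not progressing at week 8. The plan does not give c, so a range is shown. Assume all n subjects are scanned and all others progress at the week-8 scan. Then X, the number progressing there, is Binomial(n, 1 − c), and the median is fixed if X > n/2.

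| c | n = 15, P(X ≥ 8) | n = 24, P(X ≥ 13) |
|---|---|---|
| 30% | 95% | 97% |
| 40% | 79% | 79% |
| 50% | 50% | 42% |
| 60% | 21% | 11% |
| 70% | 5% | 1% |

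n = 15 is Arm B, and also Cohort 3 plus an unexpanded Arm A (6 + 9). n = 24 (6 + 18) applies only if Arm A is expanded.

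**5. What if the median is not fixed there?** Under the same assumption, after week 8 the SAP curve equals c times the curve of those who did not progress. If half of them were progression-free at 6 months, the SAP would report 0.30 × 50% = 15% to 0.70 × 50% = 35%.

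**6. Can the planning rate supply c?** Not directly. SAP 6.3 assumes stable disease in 30%, but applies a criterion of more than 16 weeks from SD onset. Subjects with shorter stable disease, and responders, would add to c, so 30% may be only a floor.

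**The case against.** The best defence is that naming the SAF may only identify the analysis set, and that the restriction was simply left out. The same phrase is used for the listings of DOR and TTR, which are restricted endpoints. Table 8 carries rows for subjects without scans that cannot apply to DOR, so the matching rows in Table 9 do not prove an intention to include everyone. The table shells are a separate document and might hold the condition. All of this bears on intent. The SAP text still yields the whole-arm curve when followed as written.

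It is also fair that little depends on the curve. The Arm A expansion uses its own stable-disease rule, PFS is reported alongside, and durations for subjects with stable disease can be rebuilt from the BOR tables and listings. That limits the severity.

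Two stronger readings are tempting and are not supported:

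- **A reader might infer that most deaths are censored.** The documents give no death counts. Deaths after iCPD follow an event, and deaths within 8 weeks of an iUPD are events under row 3. Rows 3 and 9 overlap for a death between iUPD and iCPD, with no order of precedence. Only deaths without a qualifying progression are clearly censored.
- **A reader might infer that any arm without stable disease would report 1.87 months.** That needs more than half of the scanned subjects to progress at an on-schedule week-8 scan. Such an arm could contain responders, and Protocol 6.2 allows earlier scans when clinically indicated.

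**Conclusion.** The point stands as a defect in the definition. Followed exactly, SAP 10.1.4 and Table 9 produce time to progression for the whole arm under the name of a different secondary endpoint. That conclusion rests on the text alone. The 1.87 months (1.77 to 1.97) for a subject first seen to progress at week 8 needs only an on-schedule scan and later confirmation. How far an arm's median is distorted cannot be fixed from the documents: the 95% to 5% range for n = 15 is an illustration that assumes every subject is scanned and all early progression is seen at that scan. The error is worth correcting before the final analysis, but it is a modest one in a descriptive, non-randomized trial.

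**What to change.** In SAP 10.1.4, restrict the analysis to SAF subjects with a best overall response of iSD, keeping treatment start as the origin. Three details need settling with it:

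- **Unconfirmed responses.** SAP 10.1.1 says "A BOR of iCR or iPR requires confirmation of response at least 28 days after the date of the initial response" but does not say how an unconfirmed response is then classed. State that such a subject counts as iSD for this analysis, or say where else the subject goes. Otherwise a subject could fall outside both DOR and this endpoint.
- **Table 9 rows 1 and 2.** Remove them, since a subject with best response iSD must have baseline and post-baseline assessments.
- **Table 9 rows 3 and 9.** State which takes precedence for a death after iUPD and before iCPD.

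Alternatively, keep the full SAF and rename the endpoint time to progression. The precedence of rows 3 and 9 would still need stating.

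The cost is a short SAP amendment and minor programming, with no new data. The restriction leaves fewer subjects and wider confidence intervals: at the 30% planning rate, about 0.30 × 15 = 4.5 of 15 subjects.

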10.2 Exploratory Efficacy Analyses

10.2.1 ORR per itRECIST (Phase IIa arms only)

ORR per itRECIST will be reported for injected and non-injected target lesion, separately, using the SAF set. itRECIST will be programmatically derived using data obtained from iRECIST assessments following the derivation rules provided in [APPENDIX 5. itRECIST DERIVATION RULES](#).

ORR per itRECIST will be summarized as described for ORR by iRECIST, except for presenting injected and non-injected target lesions, separately. Also, results from patients receiving 2 mg/mL and 5 mg/mL CyPep-1 will be pooled and included in addition to by cohort/arm presentation to explore a general effect of any treatment with CyPep-1 on ORR.

A double waterfall plot of maximum percentage reduction from baseline in injected and non-injected target lesion sum of diameters (mm) will be provided for the itRECIST analysis instead of the regular waterfall plot. Injected and non-injected responses will be presented on the same figure for SAF.

10.2.2 Survival

Overall survival (in months) is defined as the time from start of study treatment to the date of death:

(censoring date OR date of death – treatment start date + 1) / 30.4375.

Subjects who do not die will be censored at the last known alive date, i.e., at the date of last study visit or the latest survival follow up call, whichever occurs later. SAF will be used for the evaluation of OS.

Progression-free survival is defined as the time from treatment start until disease relapse or disease progression (based on all lesions, using iRECIST) or death due to any cause, whichever occurs earliest:

(date of iUPD followed by confirmation or death – treatment start date + 1) / 30.4375.

Event and censoring rules for PFS are detailed in [APPENDIX 2. CENSORING RULES: DOR and PFS](#). SAF will be used for the evaluation of PFS.

OS and PFS will be analyzed based on the Kaplan-Meier methods described for DOR.

OS will further be presented (both in tables and on Kaplan-Meier plots) by RMH prognostic score at baseline and GRIM-score at baseline, separately. Subjects with missing RMH prognostic score and GRIM-score values at baseline will be excluded. For the purpose of this exploratory analysis, subjects from all cohorts/arms will be pooled into one group (Total: Phase I + IIa). The analysis will be run including and excluding subjects with adrenocortical carcinoma (ACC) diagnosis. Subjects with ACC diagnosis will be identified based on coded value (i.e., MedDRA PT) of "Adrenocortical carcinoma" corresponding to *Histological type* reported on the *Primary Diagnosis* section of the *Primary Cancer eCRF* page. The aim of this analysis is to further validate the prognostic properties of RMH prognostic score and GRIM-score for population under study.

By-subject data will be listed.

10.2.3 Pharmacokinetics

PK analysis is planned via the determination of the plasma concentration (ng/mL) time profile of CyPep-1 and, if detectable, plasma drug levels are identified, the derived PK parameters will be assessed. These include area under the curve, peak plasma concentration, time to reach C_{max} , systemic clearance, elimination half-life and volume of distribution.

PK data is provided to [REDACTED]

Details on derivation of PK parameters and summaries to be created are provided in the *PK Analysis Plan* produced by [REDACTED] PK group ([REDACTED]). All PK summaries will be provided by [REDACTED] PK group in *PK Analysis Report*.

Statistical Analysis Plan

SMS-0571/CyPep-1
V3.0 Final
04-Jun-2024

10.2.4 Immunological Parameters

Immunological parameters will be analyzed using the SAF.

CD8+ T-cell Infiltration

CD8+ data are provided to [REDACTED]; details on data transfer are specified in corresponding *External Data Transfer Agreement*.

CellCarta is responsible for providing CD8+ T-cell infiltration data summaries to sponsor in accordance with the study protocol.

For this SAP, CD8+ T-cell infiltration data will only be listed.

T-cell Receptor Clonality Levels

TCR clonality data are provided to [REDACTED] via the Immunoseq tool.

Adaptive is responsible for providing T-cell receptor clonality levels data summaries to sponsor in accordance with the study protocol.

However, Simpson's clonality results in biopsy on Cycle 1 Visit 4 will be correlated to Simpson's clonality results in blood on Cycle 1 Visit 4 for the 6 subjects who had TCR data measured in both biopsy and blood. Scatter plot will be used for this analysis. Results will be displayed in pooled fashion (i.e., no presentation by cohort/arm) due to small sample size.

T-cell receptor clonality levels data will also be listed.

Tumor Microenvironment

Tumor microenvironment data are provided to [REDACTED]; details on data transfers are specified in corresponding *External Data Transfer Agreements*.

[REDACTED] are responsible for providing tumor microenvironment data summaries to sponsor in accordance with the study protocol.

However, PD-L1 expression data (Tumor Positive Score) will be presented by summary statistics for Arm B subjects at baseline in scope of this SAP.

For this SAP, tumor microenvironment data will only be listed.

Cytokine Levels

Cytokines data are provided to [REDACTED]; details on data transfer are specified in corresponding *External Data Transfer Agreement*.

Changes in cytokine levels (only for Arms A, B, and C) will be explored. [REDACTED].

The change in cytokine levels between screening and post-baseline timepoints will be assessed and estimated using paired t-tests with a 0.05 significance level. In addition to test results, the summary table will include summary statistics for cytokine levels by timepoint and for change from screening to each post-baseline timepoint.

Cytokines data will also be listed.

Peripheral Blood Phenotyping

Peripheral blood phenotyping data are provided to [REDACTED]; details on data transfer are specified in corresponding *External Data Transfer Agreement*.

Cerba Research is responsible for providing peripheral blood phenotyping data summaries to sponsor in accordance with the study protocol.

For this SAP, peripheral blood phenotyping data will only be listed.

Exploratory Analyses of Immunological Parameters

Correlation between immunological parameters and select efficacy endpoints may be explored in case immunological signals are observed. Such analyses, if carried out, will be described in an SAP amendment or in the Clinical Study Report, as applicable.

Statistical Analysis Plan

SMS-0571/CyPep-1
V3.0 Final
04-Jun-2024

10.2.5 Exploratory Subgroup Analyses

The following sub-group analyses may be carried out:

1. Analysis of subjects having received weekly vs Q2W CyPep-1 administration,
2. Analysis of subjects in Arm D corresponding to Inclusion Criteria 8e,

Analysis of subjects having received weekly vs Q2W CyPep-1 administration

Comparisons of efficacy data between subjects who received weekly and by-weekly CyPep-1 administrations may be carried out, given sufficient sample size in both groups. No such analyses are planned for this version of SAP.

Analysis of subjects in Arm D corresponding to Inclusion Criteria 8e

Exploratory analyses of subjects in Arm D corresponding to Inclusion Criteria 8e may be carried out. No such analyses are planned for this version of SAP.

10.2.6 Other Exploratory Analyses

Pharmacokinetics and Toxicity

A summary table of AEs (by SOC and PT) by cycle and cohort will be created for the PKS, split by C_{max} detectable vs not detectable.

Intratumoral Dose Concentration

Summary statistics for intratumoral dose concentration at baseline (mg/mm^3) will be presented by best overall response per iRECIST (iSD and better vs worse than iSD) and cohort/arm for the SAF. Corresponding box plots will also be created.

Intratumoral dose concentration at baseline will be calculated following the steps below:

1. For each subject, the volume of i th lesion injected at first treatment administration will be estimated using the formula of volume of sphere:

$$V_i = \frac{1}{6} \cdot \pi \cdot d_i^3$$

where d_i is the longest diameter of lesion i obtained by baseline CT scan (if CT scan is not available, then results from local measurements performed before treatment injection will be used).

2. For each subject, the intratumoral dose concentration at baseline will be calculated as:

$$Conc_{IT} = Average \left(\frac{D_i}{V_i} \right)$$

where D_i is the dose injected (mg) into i th lesion at first treatment administration and average is taken over all lesions injected at first treatment administration.

Injected Target Lesion Volume and Best Response in Injected Target Lesions per itRECIST

Injected target lesion volume is hypothesized to be correlated with injected target lesion response per itRECIST. In order to explore that relationship, the following analysis steps will be taken:

1. For each subject, the injected target lesions volume (mm^3) at baseline will be calculated as sum of volumes of all target lesions injected at baseline, based on the formula of volume of sphere:

$$V = \sum_i \frac{1}{6} \cdot \pi \cdot d_i^3$$

where d_i is the longest diameter of lesion i obtained by baseline CT scan (if CT scan is not available, then results from local measurements performed before treatment injection will be used). For this calculation, baseline can differ between different injected target lesions of the same subject following the itRECIST rules provided in [APPENDIX 5. itRECIST DERIVATION RULES](#).

2. Then, median of injected target lesion volume over all patients in SAF will be calculated and patients will be divided into two groups: low volume (\leq median) and high volume ($>$ median).
3. Finally, the itRECIST injected target lesion best response (grouped as itSD and better vs worse than itSD) will be presented by low/high volume groups for the SAF. Fisher's exact test will be used to compare distribution of response between the low and high-volume groups; p-value corresponding to the test will be presented.

The same analysis will be run excluding subjects with adrenocortical carcinoma (ACC) diagnosis. Subjects with ACC diagnosis will be identified based on coded value (i.e., MedDRA PT) of "Adrenocortical carcinoma" corresponding to *Histological type* reported on the *Primary Diagnosis* section of the *Primary Cancer eCRF* page.

Statistical Analysis Plan

SMS-0571/CyPep-1

V3.0 Final

04-Jun-2024

11 Safety Analysis

Safety will be assessed by means of physical examinations, body weight, vital signs, ECOG performance status, laboratory evaluations (hematology, biochemistry, coagulation, urinalysis), electrocardiograms (ECG), and recording of concurrent illness/therapy and adverse events. All assessments will be performed as indicated in the protocol Schedule of Assessments. Additional assessments may be performed as clinically indicated.

All safety analyses will be performed on the SAF.

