13.5 APPENDIX 5. itRECIST DERIVATION RULES

The following section is adopted from (GOLDMACHER, 2020).

For all sum of diameters (SOD) calculations below, lesions that are assessed as “too small to measure” at a specific assessment, are considered to have diameter of 5 mm at that specific assessment (as suggested by RECIST 1.1). In case a lesion is non-evaluable at a timepoint, SOD will be missing for that timepoint.

Timepoint Response: Injected and Non-Injected Target Lesions

For timepoint response per itRECIST, the rules provided in [Table 11](#) below will be used for determining injected and non-injected response.

Table 11. itRECIST Timepoint Response Categories by Lesion Category

itRECIST Response Category	Injected Target Lesions (T-I)	Non-Injected Target Lesions (T-NI)
itCR	All non-nodal lesions gone, nodal lesions <10 mm.	All non-nodal lesions gone, nodal lesions <10 mm.
itPR	≥30% decrease in sum of diameters from last imaging assessment.	≥30% decrease in sum of diameters from baseline.
itPD	≥20% increase in sum of diameters from last imaging assessment (≥5 mm absolute).	≥20% increase in sum of diameters from nadir (≥5 mm absolute).
itSD	Not enough growth for itPD & not enough shrinkage for itPR.	Not enough growth for itPD & not enough shrinkage for itPR.
NE	≥1 lesion cannot be measured.	≥1 lesion cannot be measured or has been injected.

For T-I lesions the response assessment is iterative because lesions selected for injection may vary between visits. At each assessment, the current SOD for all target lesions injected during the previous treatment visit should be compared with their SOD at the previous response assessment. The injected response assessment at given timepoint is based on SOD change from previous assessment.

For T-NI lesions, timepoint responses will only be calculated until the timepoint first T-NI lesion is injected.

Best Response: Injected and Non-Injected Target Lesions

The best response for T-I lesions is determined using the rules provided in [Table 11](#) above, but comparing the SOD based on the smallest size for each injected target lesion to the pre-injection SOD of the same lesions (instead of comparing current results with results from previous assessment).

The best response for T-NI lesions is determined based on non-injected target lesion timepoint responses using the hierarchy of itCR > itPR > itSD > itPD > NE.

Maximum Percent Reduction from Baseline: Injected and Non-Injected Target Lesions

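### SAP 10.2.6 tests a hypothesised correlation with continuous lesion volume only by a median split and Fisher's exact test, which costs substantial power for a graded effect and gives no confidence interval

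*SAP*

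**What the plan says.** SAP 10.2.6 states the idea as a correlation: "Injected target lesion volume is hypothesized to be correlated with injected target lesion response per itRECIST". It gives no direction, effect size or cut-off.

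The steps are then:
- Step 1 estimates each lesion's volume as a sphere and takes the "sum of volumes of all target lesions injected at baseline". It adds that "baseline can differ between different injected target lesions of the same subject following the itRECIST rules" in Appendix 5.
- Step 2 cuts the result: "median of injected target lesion volume over all patients in SAF will be calculated and patients will be divided into two groups", low being at or below the median.
- Step 3 groups best injected response as itSD-or-better against worse. "Fisher's exact test will be used to compare distribution of response between the low and high-volume groups", and the p-value is presented.
- A second run follows: "The same analysis will be run excluding subjects with adrenocortical carcinoma (ACC) diagnosis".

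No analysis of uncut volume is planned. No interval, alpha or sidedness is stated for this comparison.

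**The concern.** The hypothesis concerns a continuous quantity, but the test sees only which half of the sample a subject falls in. A subject just above the median counts the same as the subject with the largest tumour burden. A real gradient can therefore be missed although the data to show it are in hand.

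Fisher's test adds to the loss, because at this sample size its true error rate lies well below the nominal level. Apart from the cytokine t-tests in SAP 10.2.4, I find no other planned hypothesis test in the SAP, so readers are likely to notice this p-value. A non-significant result, with no interval beside it, could be taken as evidence against a volume effect when the test had little chance of finding one.

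**Working it through.** The plan states no power or sample size for this analysis, so there is no figure of its own to reproduce.

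**Sample size.** SAP 6.1 gives Phase I 12, Arm A 9 to 18, Arm B 15 and Arm C 9; its footnote puts Arm D at 1. The heading of SAP 10.2.1 limits itRECIST to Phase IIa, while SAP 4.3 lists Phase I itRECIST analyses as added. Both are covered:
- Phase IIa only: 9+15+9+1 = 34, up to 18+15+9+1 = 43.
- With Phase I: 12+34 = 46, up to 12+43 = 55.
- N=40 stands for a run with ACC or unevaluable subjects removed.

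**Assumptions, none from the documents.** Two-sided 5% level; log volume normal; logit(probability of itSD-or-better) = a + log(OR) × (log volume in SD units); OR 2 or 3; overall itSD-or-better 30%, 50% or 70%. Power is by simulation, 20,000 replicates per setting for N 40 to 55.

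**Graded effect, OR 2 per SD, 50% itSD-or-better:**

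| N | Fisher, split | Uncorrected chi-square, split | Rank-sum, uncut |
|---|---|---|---|
| 34 | about 20% | not tabulated | about 41% |
| 40 | 22.7% | 32.6% | 48.8% |
| 46 | 31.3% | 42.4% | 54.9% |
| 55 | 39.7% | 49.9% | 63.5% |

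Separate simulation runs gave 29% to 32% against 54% to 56% at N=46, and 40% to 41% against 63% to 65% at N=55. A logistic score test on log volume did slightly better than rank-sum in this setting (60% at N=46, 67% at N=55).

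**Where the loss comes from, N=46.** The total is 54.9 − 31.3 = 23.6 points, or 23.6/54.9 = 43% of the available power. The cut accounts for 54.9 − 42.4 = 12.5 points and Fisher's conservatism for 42.4 − 31.3 = 11.1. With no effect, for N 40 to 55, Fisher rejects 2.1% to 3.8% of the time, the chi-square 4.2% to 5.7% and the rank-sum test 4.6% to 5.0%. Over N 40 to 55, OR 2 and 3, and all three response rates, the total relative loss is 21% to 54%; the cut alone costs 13% to 33%.

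**Step effects, response 75% against 25%, Fisher on the split against rank-sum:**
- Step at the median: 80.7% against 85.0% (N=46); 89.6% against 90.8% (N=55). The cut itself costs nothing here.
- Step at the 25th percentile: 31.5% against 61.5% (N=46); 40.9% against 69.4% (N=55).
- Step at the 75th percentile: 31.6% against 61.9% (N=46); 45.7% against 69.8% (N=55).

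**Scale of volume.** With an assumed SD of 1.5 for log volume, N=46, OR 2 and a 30% rate, a linear score test on raw mm³ has 13% power, against 24% for Fisher on the split and 49% for rank-sum. For a step at the median (OR 6, 50% rate) raw mm³ gives 30% against Fisher's 62%. Volume goes with the cube of diameter and is skewed, so an uncut test must use ranks or the log scale.

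**The replacement estimate.** In 5,000 replicates for each of 27 settings, the logistic 95% CI covered the true value 95.0% to 96.4% of the time, and complete separation occurred in at most 0.02% of replicates. At OR 2 and a 50% rate the median CI was 1.03 to 4.05 (N=46) and 1.09 to 3.82 (N=55).

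**The case against.** The best defence is proportion. The analysis is exploratory, the SAP sets no alpha for it, and the 5% power framework is mine. The replacement is itself far from certain to succeed: at OR 2 it has roughly 41% to 64% power and an interval that barely excludes 1. Individual data are listed, so the gradient could be examined anyway. All of this stands and keeps the severity low. But looking at a listing afterwards is weaker than a comparison named in advance, and the better test needs nothing that is not already collected.

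Two limits on the power claim also stand. It does not extend to every uncut test, as the raw mm³ figures show. Nor does it extend to every shape: if better response (80% against 30%, assumed) is confined to the 10th to 50th volume percentiles, Fisher beats rank-sum, 54% against 45% at N=46. A correlation is most naturally read as monotone, so the claim is limited to that.

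A reader might also infer that step 1 leaves the lesion set open, or that volume is biased because some of it accrues after treatment start. The documents do not support either. If only lesions from the first administration counted, the sentence that "baseline can differ between different injected target lesions of the same subject following the itRECIST rules" would do nothing, and Appendix 5 sets each lesion's baseline just before its first injection. Where the SAP means the first administration it says so, as in the dose-concentration analysis, where the "average is taken over all lesions injected at first treatment administration". The best response in Appendix 5 is built on the same principle, "comparing the SOD based on the smallest size for each injected target lesion to the pre-injection SOD of the same lesions". Later injection of other lesions is possible under the protocol (Schedule of Assessments, footnote 24) but restricted by inclusion criteria 2 and 26 in section 4.1. No rate is given, so neither the size nor the direction of any bias can be stated. What is left is loose wording.

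Nor is the reader left with no idea of the size of the effect: the response table by volume group shows the two proportions. What is missing is an interval, and any estimate on the volume scale.

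**Conclusion.** The concern holds for step 3. The planned test is poorly matched to a correlation hypothesis with no threshold. For a monotone graded effect of OR 2 per SD of log volume and 50% itSD-or-better, it has about half to two-thirds of the power of a rank-sum test on the same data (20/41 = 49% at N=34, 40/64 = 63% at N=55). Among the monotone shapes examined, it does about as well only for a step near the median. These figures rest on assumed N, effect size, response rate and significance level; the direction of the result does not depend on which of the plausible sample sizes applies. The consequence is confined to one exploratory analysis and its repeat without ACC, with no decision rule attached and no primary or secondary endpoint touched. Severity: COULD, a cheap improvement.

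**What to change.** Replace the test in step 3, in both the all-subject run and the run without ACC, with text such as: *Uncut injected target lesion volume will be compared between subjects with itSD-or-better and those worse than itSD by a two-sided Wilcoxon rank-sum test. The odds ratio per SD of log volume, with 95% CI, will be given from logistic regression. The table by low and high volume will be shown as description, without a p-value.* The regression should not be run on raw mm³.

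Keep the lesion set and the best-response definition of Appendix 5. At most, tidy the wording of step 1 to *each injected target lesion, at its size just before its first injection*.

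The cost is a few lines of SAP text and programming, with no new data. The downsides are a wide interval and no gain if the true effect is a step at the median. Response also stays in two categories, as now planned.
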